### **7.9.2. Discontinuation from Study**

Discontinuation from study (ie, withdrawal of consent) means that the subject does not wish to receive further protocol-required treatments or undergo protocol-required procedures, and the subject does not wish to, or is unable to, continue further study participation. Subjects who discontinue from the study during follow-up should undergo the assessments listed for the Premature Termination visit ([Section 7.8](#)). It is recommended, though not mandated, that the additional follow-up assessments described in [Section 7.6](#) be conducted, with the consent of the subject. Subject data up to withdrawal of consent will be included in the analysis of the study, and where permitted, publicly available data can be included after withdrawal of consent.

### **7.9.3. Subjects Lost to Follow-up**

A subject will be considered lost to follow-up if he/she repeatedly fails to return for scheduled visits and is unable to be contacted by the study site. The following actions must be taken if a subject fails to return to the clinic for a required study visit:

- The site must attempt to contact the subject, reschedule the missed visit as soon as possible, and counsel the subject on the importance of maintaining the assigned visit schedule and ascertain whether or not the subject wishes to and/or should continue in the study.
- Before a subject is deemed lost to follow-up, the Investigator or designee must make every effort to regain contact with the subject (where possible, 3 telephone calls and, if necessary, a certified letter to the subject's last known mailing address or local equivalent methods). These contact attempts should be documented in the subject's medical record.

Should the subject continue to be unreachable, he/she will be considered to have withdrawn from the study.

## 7.10. PK Assessments

During the study, predose plasma samples will be collected from all subjects to explore the PK profile of ABI-H0731 and NrtI following combination treatment in subjects with CHB. Additionally, postdose and post-treatment samples will be collected. The timing of PK sample collection is outlined in [Table 7](#). Additional details regarding the collection, processing, storage, and shipment of PK samples is described in the Laboratory Manual.

**Table 7: Pharmacokinetic Sample Collection**

Time period	Time relative to study drug administration a	Time relative to study drug administration b
Treatment	Predose	Day 1, Weeks 4, and 48
	30 min to 2 hours postdose	Weeks 2, 8, 12, 24, and 28
	2 to 4 hours postdose	Day 1
	4 to 6 hours postdose	Weeks 16 and 20
Follow-up	Collect at same time with other central labs	At Unscheduled and Premature Termination c Visits and the Week 4 Post Treatment Follow-up visit

a If the subject self-administers the study drug outside the study clinic, a pharmacokinetic sample should be collected during the next in-clinic visit with documentation of date and time of the dose in the subject's source documents.

b Sample collection times are targeted times. Samples collected outside of these targeted times will not be considered protocol deviations. The actual sample collection date/time should be accurately recorded on source documentation.

c A pharmacokinetic sample should also be collected if an unscheduled or premature termination visit is performed.

## 7.11. End of Study Definition

The study will be completed when the last subject completes the 24-week, post-treatment follow-up period, or is considered "lost to follow-up," ([Section 7.9.3](#)) whichever is later.

## 7.12. Resistance Monitoring

During the Screening procedures, all subjects will be evaluated for HBV polymerase mutations as described in [Appendix 2](#). Subjects having any of these mutations will be excluded from study participation.

To assess for viral resistance during the study, serum samples from subjects at each visit will be collected ([Section 7](#)). Samples from those subjects with evidence of nonresponse to treatment, such as viral breakthrough (ie, >1 log10 increase in HBV DNA from on-treatment nadir) will be selected for HBV gene sequencing, with sequence comparisons to Baseline sequences, as well as comparisons to HBV gene sequences from subjects who received PBO and HBV database sequences.

## 8. ADVERSE EVENTS

An AE is any untoward medical occurrence in a study subject administered an investigational product(s) regardless of the causal relationship with treatment.

An AE, therefore, can be any unfavorable and unintended sign (including laboratory finding), symptom, or disease temporally associated with participation in an investigational study, whether or not considered drug-related. In addition to new events, any increase in the severity or frequency of a pre-existing condition that occurs after the subject signs the ICF for participation is considered an adverse event. This includes any side effect, injury, toxicity, or sensitivity reaction.

### 8.1. Documenting Adverse Events

Adverse events will be monitored throughout the entire study. Investigators will ask the subject at each visit if they have experienced any untoward effects since the last study visit. All AEs will be entered in the eCRFs provided: a description of the event, severity, time of occurrence, duration, any action (eg, treatment and follow-up tests), and the outcome should be provided along with the Investigator's assessment of the relationship to the study treatment (refer to the eCRF completion guidelines).

Adverse events will be recorded from the date informed consent is signed through end of study (completion of follow-up period).

### 8.2. Assessment of Intensity

The severity of each AE and laboratory abnormality is to be assessed by the Investigator according to the modified Division of AIDS Table for Grading the Severity of Adult and Pediatric AEs ([Appendix 3](#)), which grades the severity of clinical AEs and laboratory abnormalities in a 4-category system.

For AEs not included in [Appendix 3](#), the following guidelines will be used to describe severity:

- **Mild (Grade 1):** Mild symptoms causing no or minimal interference with usual social and functional activities with intervention not indicated
- **Moderate (Grade 2):** Moderate symptoms causing greater than minimal interference with usual social and functional activities with intervention indicated
- **Severe (Grade 3):** Severe symptoms causing inability to perform usual social and functional activities with intervention or hospitalization indicated (Of note, the term "severe" does not necessarily equate to "serious")
- **Life-threatening (Grade 4):** Potentially life-threatening symptoms causing inability to perform basic self-care functions with intervention indicated to prevent permanent impairment, persistent disability, or death

Note that an AE or laboratory abnormality that is life-threatening as it exists constitutes an SAE.

### 8.3. Assessment of Causality

All AEs must have their relationship to study intervention assessed by the clinician who examines and evaluates the subject based on temporal relationship and his/her clinical judgment. Each AE must be recorded in the source documentation, whether serious or not serious. For the purposes of this study each event is to be assessed with regard to the following causality categorizations, in the Investigator's considered judgment:

- **Not related:** An AE with sufficient evidence to accept that there was no causal relationship to administration of study drug (eg, no temporal relationship because the study drug was administered after the onset of the event, an investigation showed that study drug was not administered, another cause was proven).
- **Related:** An AE occurred in a plausible time relationship to administration of study drug and that could not be explained by a concurrent disease or other drugs or events. The response to withdrawal of the drug (dechallenge) was clinically reasonable.

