### **9.4. Management of On-treatment and Post-treatment ALT Elevations**

All subjects participating in the study will be closely monitored for ALT elevations and/or signs of potential decline in hepatic function. Subjects experiencing ALT elevations  $\geq 2 \times$  Baseline or on-treatment nadir and  $> 2 \times$  ULN during study treatment or during post-treatment follow-up should be closely monitored with regular unscheduled visits every 1 to 2 weeks at the discretion of the Investigator. For these subjects, at each timepoint, an Unscheduled Visit should be conducted with completion of assessments as described in [Section 7.7](#). Additionally, the following guidance is provided for management of subjects with ALT elevations:

- All subjects with an ALT elevation on treatment, defined as ALT  $> 2 \times$  Baseline or on-treatment nadir and  $\geq 10 \times$  ULN, should have the ALT findings confirmed within 3 days of receipt of the original results. To confirm the ALT finding, the subject should return to the clinic for an Unscheduled Visit and undergo all assessments as noted in [Section 7.7](#) (Unscheduled Visit).
- If the ALT elevation is confirmed, then an additional Unscheduled Visit will be performed to further evaluate the subject. At this visit, the following laboratory tests will be performed: ALT, AST, total bilirubin (if total bilirubin is elevated, reflex to Direct Bilirubin), serum albumin, HBV DNA, and quantitative HBV serologies (HBeAg [reflex qualitative HBeAg if quantitative HBeAg is negative] and HBsAg [reflex qualitative HBsAg if quantitative HBsAg is negative]), HAV IgM, HCV RNA, HDV RNA, and HEV IgM.
  - If an intercurrent illness is determined to be causal, subjects with an ALT elevation without declining hepatic function and without contraindications may continue

treatment and the intercurrent illness should be treated as deemed medically appropriate by the Investigator.

- Subjects with an ALT elevation without declining hepatic function and without contraindications may continue treatment with study drug under close observation.

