- If ALT is rising at the confirmatory visit, subjects should return for an **Unscheduled Visit** every 2 to 5 days until the ALT elevation has stabilized. At these visits the following laboratory tests will be performed: ALT, AST, total bilirubin (if total bilirubin is elevated, reflex to Direct Bilirubin), serum albumin, INR, HBV DNA, and quantitative HBV serologies (HBeAg [reflex qualitative HBeAg if quantitative HBeAg is negative] and HBsAg [reflex qualitative HBsAg if quantitative HBsAg is negative]). Subjects whose ALT has stabilized should continue to be monitored weekly (or more frequently, as deemed necessary by the treating physician) until ALT values return to normal or Baseline levels.
  - Subjects with an ALT elevation without declining hepatic function and without contraindications should discontinue study drug if the ALT remains persistently elevated for >4 weeks
- Subjects with confirmed ALT elevation with evidence of declining hepatic function should be discontinued from study treatment. This is defined as:
  - ALT elevation  $\geq 2 \times$  Baseline or nadir and  $> 2 \times$  ULN AND
    - Direct bilirubin increase to  $\geq 2 \times$  Baseline and  $\geq 2 \times$  ULN OR
    - Albumin decline  $\geq 0.5$  g/dL OR INR  $> 2 \times$  Baseline OR
    - Symptoms of liver inflammation (eg, fatigue, weakness, lack of appetite, nausea, vomiting, jaundice, or discolored feces)
- Subjects with evidence of declining hepatic function should return for an **Unscheduled Visit** every 2 to 5 days until the relevant laboratory values stabilize. Subjects whose hepatic function has stabilized should continue to be monitored weekly (or more frequently as deemed necessary by the Investigator) until the relevant laboratory values return to normal or Baseline.
- **Post-treatment ALT Elevation**

Following cessation of study drug treatment under this protocol all subjects will be closely followed for ALT elevations and/or signs of potential decline in hepatic function. This applies to all subjects whether they prematurely discontinue study drug or complete the study per protocol. Any subject with a post-treatment ALT elevation without evidence of declining hepatic function or a post-treatment ALT elevation with evidence of declining hepatic function as defined above, will be evaluated as noted above.

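### Do the two causality definitions in protocol section 8.3 leave some adverse events with no rating, and does the plan need to change for it?

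*Combined protocol and SAP*

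**What the plan says.** Protocol section 8.3 offers two ratings and no third.

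- **Related** asks for plausible timing and an event "that could not be explained by a concurrent disease or other drugs or events". A separate sentence adds: "The response to withdrawal of the drug (dechallenge) was clinically reasonable". It has no qualifier for events during which drug was not stopped.
- **Not related** is "An AE with sufficient evidence to accept that there was no causal relationship to administration of study drug". Three illustrations follow, one of them a proven other cause.

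The same section requires an assessment for every AE, made "based on temporal relationship and his/her clinical judgment". Section 8.1 asks for the Investigator's "assessment of the relationship to the study treatment (refer to the eCRF completion guidelines"); those guidelines are not among the documents.

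Section 9.4 governs ALT elevations. Where hepatic function is not declining, subjects "may continue treatment with study drug under close observation", but they "should discontinue study drug if the ALT remains persistently elevated for >4 weeks". It also says: "Subjects with confirmed ALT elevation with evidence of declining hepatic function should be discontinued from study treatment".

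The rating is used in the drug-related subset of TEAE summaries planned in protocol 10.3.7.1. SAP 7.1.3 takes Related from the Investigator's selection on the form and lists an unrecorded relationship as missing. SAP 1 and SAP 3 state that the trial was terminated with 2 subjects randomized and that only listings will be made.

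**The concern.** A two-way rating should cover every case, and this one does not on its face. Having no possible alternative explanation and having sufficient evidence against causality are far apart, and many real events fall between them. The population makes this likely: every subject has chronic hepatitis B and takes an NrtI, so a concurrent disease and another drug are always candidate explanations, above all for a rise in ALT. If drug continues through such a rise, there is no withdrawal to which a response can be judged.

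The protocol's own background section (2.2.3.2.1) describes an event of this type in Study 211: a Grade 3 ALT elevation thought possibly related, which improved while treatment went on. The rating scale of that study is not given, so this shows the kind of event and not an error there.

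At stake would be the drug-related AE table. Sites could place similar events in different categories, and the text does not say in which direction the count would move.

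**Working it through.** There is no figure to reproduce. The check sets the two definitions against each type of plausibly timed AE, with the dechallenge sentence read first as a required condition and then as description only.

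| Other cause | Study drug | Dechallenge required | Dechallenge descriptive |
|---|---|---|---|
| None | Stopped, reasonable response | Related | Related |
| None | Stopped, response not reasonable | Neither | Related |
| None | Continued | Neither | Related |
| Possible, unproven | Any | Neither | Neither |
| Proven | Any | Not related | Not related |

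1. The fourth row falls outside both definitions on either reading. The gap in the wording is therefore real. The illustrations under Not related are not a closed list, so an Investigator may find the evidence sufficient without proof. That narrows the row but does not remove it.
2. Rows two and three fall outside only if dechallenge is a condition. For ALT elevations, section 9.4 limits row three: drug stops if the elevation lasts more than 4 weeks or if hepatic function declines. Sections 4.1 and 4.3 also end ABI-H0731 at Week 96. Row three is then confined to events that resolve, or are rated, while drug continues.
3. The rows are types of event, not frequencies. The documents give no frequencies, so the number of rows in the gap does not measure its size.

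Next, where the rating is used:

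- **Primary safety endpoint (3.2.1):** all AEs, premature treatment discontinuations and abnormal laboratory results. No causality filter.
- **All-AE and SAE tables (10.3.7.1):** no causality filter.
- **SAE reporting (9.2):** all SAEs within 24 hours. No causality filter.
- **Regulatory notification for ALT (9.4):** triggered by the number of subjects meeting ALT criteria. No causality filter.
- **Drug-related TEAE table (10.3.7.1):** uses the rating, but is not produced under SAP 3.
- **AE listing (SAP 7.1.3 and 7.1.6):** uses the rating, for the 2 randomized subjects.
- **Post-study pregnancy-related SAEs (8.7.1):** a reporting duty that depends on relatedness, but by its own standard of reasonable relatedness and not by the two categories of 8.3.

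In this trial, then, the 8.3 categories reach one field of one listing. The documents do not show that either subject had any AE, still less one of the fourth-row type.

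**The case for a change.** The strongest case for a change is that judgment lets a site pick a rating but gives no common rule, so two Investigators may rate the same event differently. The situation is foreseeable in this population, and the cost is low: one sentence in the synoptic report, and better wording if the protocol is amended or reused. Section 8.7.1 shows that the protocol already has a more workable phrase for relatedness.

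Part of this stands. The definitions are not complements, and some variation between raters is possible. Two things weaken it. Blank ratings are an unlikely result, because 8.3 makes assessment mandatory; the SAP's rule for a missing relationship matches its rule for missing severity in 7.1.2 and is an ordinary convention for empty fields. And the eCRF completion guidelines may already hold a default, which cannot be checked here.

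The proposed sentence would say only that ratings followed the protocol, which a reader would assume. Whether drug had been stopped can be read from the exposure listing already planned in SAP 4.2. A rating based on reasonable possibility is also a trade-off: it would class some events due to hepatitis B or the NrtI as related.

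**Conclusion.** The wording of 8.3 is loose, but no change to the plan is warranted, because nothing would be gained. Investigators must still choose one of two ratings, so the possible effect is inconsistency between raters and not an event that cannot be recorded. No endpoint, SAE report or ALT notification uses these categories. With 2 subjects and listings only, the effect is at most one field in one listing. New wording would not revise ratings already made, and no conclusion of the trial rests on them.

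This assumes that the trial is reported as the SAP describes. Had the planned trial of about 40 subjects run to its TEAE tables, the drug-related subset would have been open to this inconsistency, by an amount the documents do not allow one to estimate. If the text is carried into another protocol, an editor would sensibly make one category the complement of the other and treat dechallenge as supporting evidence where drug was withdrawn.

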#### **8.4. Expectedness**

An AE is considered “unexpected” if it is not listed in the IB or is not listed at the specificity or severity that has been observed. The CRO and Sponsor Medical Monitors will be responsible for determining whether an AE is expected or unexpected.

#### **8.5. Abnormal Laboratory Test Values**

In the event of abnormal laboratory test values, the tests should be repeated immediately. If the Investigator considers the abnormality to be clinically significant, it should be reported as an AE and followed up until it returns to the normal range and/or an adequate explanation of the abnormality is found.

#### **8.6. Adverse Event Follow-up**

After the initial AE or SAE report, the Investigator will follow-up proactively on each subject and provide further information to the CRO/Sponsor on the subject’s condition. During the study, all AEs or SAEs should be followed to resolution unless the event is considered by the Investigator to be unlikely to resolve due to the subject’s underlying disease, or the subject is lost to follow-up.

#### **8.7. Pregnancy**

##### **8.7.1. Female subjects who become pregnant**

Any female subject who becomes pregnant while participating in the study will discontinue the study drug(s) immediately.

The Investigator will collect pregnancy information on any female subject who becomes pregnant while participating in this study, including the 24-week follow-up period. The initial information will be recorded on the Pregnancy Reporting form and submitted to the CRO Pharmacovigilance group within 24 hours of learning of a subject’s pregnancy. Refer to the Study Reference Manual for contact information for reporting a pregnancy.

The subject will be followed to determine the outcome of the pregnancy. The Investigator will collect follow-up information on the subject and the neonate and the information will be forwarded to the Sponsor. Generally, follow-up will not be required for longer than 6 to 8 weeks beyond the estimated delivery date. Any termination of pregnancy will be reported, regardless of fetal status (presence or absence of anomalies) or indication for the procedure.

While pregnancy itself is not considered to be an AE or SAE, any pregnancy complication or elective termination of a pregnancy for medical reasons will be reported as an AE or SAE. A spontaneous

abortion (occurring at <22 weeks gestational age) or still birth (occurring at >22 weeks gestational age) is always considered to be an SAE and will be reported as such.

Any post-study pregnancy related SAE considered reasonably related to the study drug(s) by the Investigator will be reported to the Sponsor. While the Investigator is not obligated to actively seek this information in former study subjects, he or she may learn of an SAE through spontaneous reporting.

#### **8.7.2. Male subjects with partners who become pregnant**

The Investigator will conduct due diligence to collect pregnancy information on any male subject's female partner who becomes pregnant while the male subject is participating in this study. This applies only to male subjects who receive the study drug.

After obtaining the necessary signed informed consent from the pregnant female partner directly, the Investigator will record pregnancy information on the Pregnancy Reporting form and submit it to the CRO Pharmacovigilance group within 24 hours of learning of the partner's pregnancy. The female partner will also be followed to determine the outcome of the pregnancy. Information on the status of the mother and child will be forwarded to the Sponsor. Generally, the follow-up will be no longer than 6 to 8 weeks following the estimated delivery date. Any termination of the pregnancy will be reported regardless of fetal status (presence or absence of anomalies) or indication for the procedure. Refer to the Study Pharmacy Manual for contact information for reporting a pregnancy.

## **9. SERIOUS ADVERSE EVENTS**

### **9.1. Definition of SAE**

An SAE is any event that meets any of the following criteria:

- Death
- Life-threatening
- Inpatient hospitalization or prolongation of existing hospitalization
- Persistent or significant disability/incapacity
- Congenital anomaly/birth defect in the offspring of a subject who received ABI-H0731
- Other: Important medical events that may not result in death, be life-threatening, or require hospitalization, may be considered an SAE when, based upon appropriate medical judgment, they may jeopardize the subject and may require medical or surgical intervention to prevent one of the outcomes listed in this definition. Examples of such events are:
  - Intensive treatment in an emergency room or at home for allergic bronchospasm
  - Blood dyscrasias or convulsions that do not result in inpatient hospitalization
  - Development of drug dependency or drug abuse

